5.2 Exclusion Criteria

Patients meeting any of the following exclusion criteria are not to be enrolled in the study:

1. Female patients who are lactating or have a positive serum pregnancy test during the

screening period.

2. Failure to have fully recovered (ie, \leq Grade 1 toxicity) from the reversible effects of prior chemotherapy.
3. Major surgery, including craniotomy, within 14 days before enrollment.
4. Radiotherapy of brain tumor within 3 months before enrollment.
5. Infection requiring systemic antibiotic therapy or other serious infection within 14 days before study enrollment.
6. Evidence of current uncontrolled cardiovascular conditions, including uncontrolled hypertension, uncontrolled cardiac arrhythmias, symptomatic congestive heart failure, unstable angina, or myocardial infarction within the past 6 months.
7. Systemic treatment, within 14 days before the first dose of ixazomib, with strong inhibitors of CYP1A2 (fluvoxamine, enoxacin, ciprofloxacin), strong inhibitors of CYP3A (clarithromycin, telithromycin, itraconazole, voriconazole, ketoconazole, nefazodone, posaconazole) or strong CYP3A inducers (rifampin, rifapentine, rifabutin, carbamazepine, phenytoin, phenobarbital), or use of Ginkgo biloba or St. John's wort.
8. Ongoing or active systemic infection, active hepatitis B or C virus infection, or known human immunodeficiency virus (HIV) positive.
9. Any serious medical or psychiatric illness that could, in the investigator's opinion, potentially interfere with the completion of treatment according to this protocol.
10. Known allergy to any of the study medications, their analogues, or excipients in the various formulations of any agent.
11. Known GI disease or GI procedure that could interfere with the oral absorption or tolerance of ixazomib including difficulty swallowing.
12. Diagnosed or treated for another malignancy within 2 years before study enrollment or previously diagnosed with another malignancy and have any evidence of residual disease. Patients with nonmelanoma skin cancer or carcinoma in situ of any type are not excluded if they have undergone complete resection.
13. Patient has \geq Grade 3 peripheral neuropathy, or Grade 2 with pain on clinical

examination during the screening period.

14. Participation in other clinical trials utilizing other therapeutic investigational agents not included in this trial, within 30 days of the start of this trial and throughout the duration of this trial.
15. Patients that have previously been treated with ixazomib, or participated in a study with ixazomib whether treated with ixazomib or not.

6. STUDY DRUG

6.1 Description of Investigational Agents

Ixazomib Capsules

The ixazomib drug product is provided in strengths of 4.0-, 3.0-, and 2.3-mg and 2.0-, 0.5-, and 0.2 mg capsules as the active boronic acid. The different dose strengths are differentiated by both capsule size and color as described below:

Dose Strength	Capsule Size	Capsule Color
4.0 mg	Size 4	Ivory
3.0 mg	Size 3	Light gray
2.3 mg	Size 2	Light pink
2.0 mg	Size 2	Swedish orange
0.5 mg	Size 3	Dark green
0.2 mg	Size 4	White opaque

For additional details, please see the ixazomib IB.

6.2 Study Drug Administration

Ixazomib Administration

All protocol-specific criteria for administration of study drug must be met and documented before drug administration. Study drug will be administered or dispensed only to eligible patients under the supervision of the investigator or identified subinvestigator(s). Patients should be monitored for toxicity, as necessary, and doses of ixazomib should be modified as needed to accommodate patient tolerance to treatment; this may include symptomatic treatment, dose interruptions, and adjustments of ixazomib dose (see Section 6.3).

Capsules of ixazomib will also be referred to as study drug. Study drug will be supplied by Millennium as capsules of 0.2-, 0.5-, and 2.0 mg, or as capsules of 2.3-, 3.0- and 4.0 mg ixazomib.

The prescribed administration of the ixazomib dose in this study is one 4.0 mg dose approximately 3 hours prior to surgery. No further doses of ixazomib will be administered. The dose will be dispensed by the Emory University Hospital Research Pharmacy and administered by the PI who will document the time of administration, the dose, and toleration of the dose in the operative dictation. The patient will be in the preoperative waiting room and then the preoperative holding area after administration while being prepared for surgery. As there is only one dose used in this study, and it will be documented as part of the surgical procedure, no drug diary will be used.

Patients will be instructed to swallow ixazomib capsules whole, with water, and not to break, chew, or open the capsules. Study drug should be taken on an empty stomach (no food or drink) as they will have been NPO since midnight on the day surgery in preparation for general anesthesia. Each capsule should be swallowed separately with a sip of water. A total of approximately 8 ounces (240 mL) of water should be taken with the capsules.

Ixazomib Destruction

Investigational ixazomib (expired or end of study) should be destroyed on site according to the institution's standard operating procedure. Be sure to document removal and destruction on drug accountability logs.

Anesthetic agents, corticosteroids, anticonvulsants, antibiotics and other supportive agents will be administered during and after the surgical procedure (respecting those not allowed in the exclusion criteria list item number 8 above).

6.3 Excluded Concomitant Medications and Procedures

The following medications are prohibited from 14 days prior to the dose of ixazomib to 7 days after the dose of ixazomib, ie. the study period.

Systemic treatment with any of the following metabolizing enzyme inhibitors is not permitted during the study period as these drugs may interfere with the evaluation of the pharmacokinetics of ixazomib:

- Strong inhibitors of CYP1A2: fluvoxamine, enoxacin, ciprofloxacin

- Strong inhibitors of CYP3A: clarithromycin, telithromycin, itraconazole, voriconazole, ketoconazole, nefazodone, and posaconazole

Systemic treatment with any of the following metabolizing enzyme inducers should be avoided during the study period, unless there is no appropriate alternative medication for the patient's use as these drugs may interfere with the evaluation of the pharmacokinetics of ixazomib:

- Strong CYP3A inducers: rifampin, rifapentine, rifabutin, carbamazepine, phenytoin, and phenobarbital

Excluded foods and dietary supplements include St. John's wort and Ginkgo biloba

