1. BACKGROUND AND STUDY RATIONALE

1.1 Scientific Background

1.1.1 Disease Under Treatment

Glioblastoma, the most common primary tumor of the brain in adults, is rarely associated with cure or even control.[1] Advances in surgical care and radiation planning have improved safety, and the addition of temozolomide to initial therapy has added some months to overall survival.[2]

At progression bevacizumab extends time to further imaging progression, but not overall survival. Having said this, average overall survivals are still in the range of 12-14 months. This clearly leaves room for improvement by exploring other therapeutic modalities. Standard cytotoxic agents have been studied from a number of standpoints and their effect has probably been maximized.[3, 4, 5]

Bortezomib, a proteasome inhibitor, has been evaluated in preclinical and clinical studies with promising results, as a single agent or in combination with temozolomide and radiation therapy. As a single agent at recurrence, partial responses have been observed.[6] Additionally, bortezomib appears to enhance radiation effects in these tumors [7, 8]. In a phase I study of 66 patients with primarily recurrent glioblastoma the maximum tolerated dose in those not taking enzyme-inducing anti-seizure drugs was 1.70 mg/ m² based on grade 3 thrombocytopenia, sensory neuropathy and fatigue. In the group taking enzyme-inducing anti-seizure drugs escalation was terminated at 2.5 mg/m² without meeting meet the maximum tolerated dose criteria. However, proteasome inhibition in this group did not change at significantly at doses above 1.50 mg/m² for those not taking enzyme-inducing anti-seizure drugs and above 1.90 mg/m² for those taking enzyme-inducing anti-seizure drugs. This suggests that further escalations beyond those studied in this protocol would be unlikely to increase the biologic effect of this proteasome inhibitor. Two partial responses were observed.[9] Based on this information there appears to be a potential role for proteasome inhibitors in the management of progressive glioblastoma and this warrants the investigation at hand here.=.

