Metabolism appears to be the major route of elimination for ixazomib, and urinary excretion of the parent drug is negligible (< 5% of dose). In vitro studies indicate that ixazomib is metabolized by multiple cytochrome P450s (CYPs) and non-CYP enzymes/proteins. The rank order of relative biotransformation activity of the 5 major human CYP isozymes was 3A4 (34.2%) > 1A2 (30.7%) > 2D6 (14.7%) > 2C9 (12.1%) > 2C19 (< 1%). Ixazomib is not an inhibitor of CYPs 1A2, 2C9, 2C19, 2D6, or 3A4 nor a time-dependent inhibitor of CYP3A4/5. The potential for ixazomib treatment to produce drug-drug interactions (DDIs) via CYP inhibition is inferred to be low. However, there may be a potential for DDIs with a concomitant strong CYP3A4 or CYP1A2 inhibitor or inducer because of the potential for first-pass metabolism when ixazomib is administered via the PO route and because of the moderate contribution of CYP3A4- and CYP1A2-mediated metabolism of ixazomib in human liver microsomes. Ixazomib may be a weak substrate of P-glycoprotein (Pgp), breast cancer resistance protein (BCRP), and multidrug resistance associated protein (MRP2) efflux pump transporters. Ixazomib is not an inhibitor of Pgp, BCRP, and MRP2. The potential for DDIs with substrates or inhibitors of Pgp, BCRP, and MRP2 is, therefore, inferred to be low. Clinical Study C16009 (Arm 1) with ketoconazole, a strong CYP3A4 inhibitor, showed a 2-fold increase in area under the plasma concentration versus time curve (AUC) in the presence of ketoconazole. This resulted in the continued exclusion of strong CYP3A4 inhibitors in ongoing/planned clinical studies.

Further details on these studies are provided in the IB.

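### Sections 5.2 and 6.3 give different rules for strong CYP3A inducers in the 14 days before the dose, and the concentration analysis has no flag for an exposed patient

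*Combined protocol and SAP*

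**What the plan says.** Section 5.2 opens with an absolute rule: "Patients meeting any of the following exclusion criteria are not to be enrolled in the study". Item 7 covers "Systemic treatment, within 14 days before the first dose of ixazomib" and lists, beside CYP1A2 and CYP3A inhibitors, "strong CYP3A inducers (rifampin, rifapentine, rifabutin, carbamazepine, phenytoin, phenobarbital". It states no exception.

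Section 6.3 begins by calling the drugs that follow "prohibited from 14 days prior to the dose of ixazomib to 7 days after the dose of ixazomib", and defines that interval as the study period. It bars the inhibitors outright. For the inducers, the same six by name, it says that they "should be avoided during the study period, unless there is no appropriate alternative medication". Its stated reason for both groups is possible interference with the pharmacokinetic evaluation.

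Section 6.2 provides for anticonvulsants and other supportive drugs during and after surgery, "respecting those not allowed in the exclusion criteria list item number 8 above". Item 8 in Section 5.2 is about systemic infection, hepatitis and HIV. The drug list is item 7.

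**The concern.** The primary endpoint (Section 3.1) is ixazomib concentration in tumor, blood and plasma, in three patients (Section 4.2). The drug is given by mouth, and Section 1.4 warns that "there may be a potential for DDIs with a concomitant strong CYP3A4 or CYP1A2 inhibitor or inducer", citing first-pass metabolism. By the protocol's own reasoning, then, inducer exposure before the dose could change the quantity being measured.

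Two sections answer differently whether such a patient may be treated, and staff could follow either. The question is not remote in this disease: Section 1.1.1 describes a bortezomib study, mainly in recurrent glioblastoma, that had a separate group taking enzyme-inducing anti-seizure drugs.

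If such a patient were dosed, nothing in the plan would mark that patient's values. The screening list in Section 6.11 contains no concomitant-medication record. Section 7.1 relates concentration to demographic and tumor factors, not to medication. The replacement and discard rules in Sections 6.12, 7.1.1 and 7.1.3 deal with missed dosing, surgery or visits, unusable samples and missing data. Section 6.12 also lets the investigator withdraw a patient for a protocol violation, but whether inducer use under the 6.3 exception is a violation is exactly what the two sections leave open.

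**Working it through.** No figure in the plan depends on this point, and the sample size of three rests on clinical judgment (Section 7.1.1), so there is no plan calculation to reproduce. The check is a comparison of texts, followed by a small illustration.

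**Step 1. The two rules side by side.**

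| | Section 5.2 item 7 | Section 6.3 |
|---|---|---|
| Drugs | rifampin, rifapentine, rifabutin, carbamazepine, phenytoin, phenobarbital | the same six |
| Window | 14 days before the dose | 14 days before to 7 days after the dose |
| Force | excluded, no exception | introduced as prohibited, then allowed if no suitable alternative exists |

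The windows overlap in the 14 days before the dose. There the rules conflict: a patient on phenytoin with no alternative is ineligible under 5.2 and acceptable under 6.3. The exception cannot be read as applying only after dosing, because 6.3 states when its window opens. Section 6.3 also conflicts with itself, since its opening line and its inducer paragraph differ in force.

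**Step 2. Where the conflict can and cannot matter.**

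- Before the dose: 5.2 and 6.3 disagree, and exposure could affect every sample.
- From the dose to the last blood or tumor sample: item 7 no longer applies, so only 6.3 and the wrong pointer in 6.2 govern.
- After the last sample: an inducer started then cannot change the measured concentrations.

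**Step 3. Illustration of size.** The documents give no effect of an inducer on ixazomib. Their only quantified interaction is a 2-fold rise in AUC with ketoconazole, an inhibitor (Section 1.4). Assume three otherwise equal patients with concentration 1, one of whom has a fraction r of that. Then:

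- mean = (1 + 1 + r)/3, a fall of (1 − r)/3;
- standard error from that one patient alone = (1 − r)/3, because the standard deviation of (1, 1, r) is (1 − r)/√3 and dividing by √3 gives (1 − r)/3.

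| Assumed r | Mean | Fall in mean | Standard error |
|---|---|---|---|
| 0.75 | 0.917 | 8.3% | 0.083 |
| 0.50 | 0.833 | 16.7% | 0.167 |
| 0.25 | 0.750 | 25.0% | 0.250 |

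With three tumor samples from every patient, the mean from the random-effects model in Section 7.1 is the average of the three patient means, so the same arithmetic applies to it.

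**The case against.** The best defense is that eligibility already closes the pre-dose route. Section 6.2 gives study drug only to eligible patients and requires the criteria to be met and documented first. Section 4.2 starts enrollment at ixazomib administration, so item 7 applies up to the dose. Section 6.3 nowhere says that it waives an exclusion. This stands: with 5.2 strictly applied, no pre-dose inducer user enters. It does not remove the contradiction, because 6.3 sets its own rule for the same days.

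It is also fair that results are tabulated and that each tumor site is analyzed separately (Sections 7.1 and 7.1.5). With three patients, a low one would be visible. But the tables would not show that an inducer was the likely reason.

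Three stronger readings are tempting, and the documents do not support them.

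- A reader might assume that 10-30% of candidates take an inducer and compute 1 − (1 − p)³, a 27-66% chance that at least one of three is affected. That ignores the bar in 5.2 and the no-alternative condition in 6.3, and the documents give no prevalence. It is not the risk under this protocol.
- A reader might infer that one induced patient could produce a finding of no measurable drug. No quantification limit is given, and one low patient does not erase measurable samples in the other two.
- A reader might take the anti-seizure-drug result in Section 1.1.1 as evidence of the effect. There the maximum tolerated dose was 1.70 mg/m² without inducers, and escalation ended at 2.5 mg/m² with them, short of the tolerability criteria. Those are dose limits for bortezomib, not ixazomib concentrations.

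Finally, the pointer error in 6.2 concerns drugs given during and after surgery, once ixazomib has been taken. It is a separate slip and does not show pre-dose exposure.

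**Conclusion.** The inconsistency is certain from the text: same six drugs, same 14 days, unconditional in 5.2 and conditional in 6.3, with a wrong item number in 6.2. It should be settled before anyone is enrolled, because it touches the primary endpoint in a study of three.

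The effect on results is conditional and cannot be sized from the documents. It arises before the dose only if 6.3 is followed over 5.2. The 17-25% fall in the mean assumes exactly one exposed patient, a concentration of 25-50% of usual in that patient, and no other difference between patients. Section 7.1.1 expects tumors to differ, so the last assumption is a simplification. The plan also measures concentrations around surgery and computes no formal pharmacokinetic parameters (Section 7.1.5), so an effect on overall exposure need not carry over in the same proportion.

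**What to change.** 1. Reconcile Section 5.2 item 7 with Section 6.3, including the opening line of 6.3, so that one rule applies before the dose. Which rule that is, and how it continues after the dose, is for the sponsor's clinicians.
2. Correct the reference in Section 6.2 from item 8 to item 7.
3. Record for each patient any strong CYP3A inducer taken in the 14 days before the dose and up to the last blood or tumor sample.
4. State in Section 7.1 that, if an exposed patient is dosed, that patient is flagged in the concentration tables and the descriptive summary is shown with and without them. With two patients left, the second summary is only descriptive, but it lets a reader see how far the result rests on the exposed one.

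The cost is small wording changes in Sections 5.2, 6.2, 6.3 and 7.1, one recorded item and one listing flag. Sample size, visits and samples stay as they are.

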6.4 Permitted Concomitant Medications and Procedures

The following medications and procedures are permitted during the study:

- Antiemetics, including 5-HT₃ serotonin receptor antagonists, may be used at the discretion of the investigator.
- Loperamide or other antidiarrheal should be used for symptomatic diarrhea at discretion of the investigator. The dose and regimen will be according to institutional guidelines. IVF should be given to prevent volume depletion.
- Patients should be transfused with red cells and platelets as clinically indicated and according to institutional guidelines.
- Supportive measures consistent with optimal patient care may be given throughout the study.

6.5 Precautions and Restrictions

- Fluid deficit should be corrected before initiation of treatment and during treatment with ixazomib.

Pregnancy

It is not known what effects ixazomib has on human pregnancy or development of the embryo or fetus. Therefore, female patients participating in this study should avoid becoming pregnant, and male patients should avoid impregnating a female partner. Nonsterilized female patients of

reproductive age group and male patients should use effective methods of contraception through defined periods during and after study treatment as specified below.

Female patients must meet 1 of the following:

- Postmenopausal for at least 1 year before the screening visit, or
- Surgically sterile, or
- If they are of childbearing potential, agree to practice 2 effective methods of contraception from the time of signing of the informed consent form through 90 days after the last dose of study drug, or
- Agree to practice true abstinence, when this is in line with the preferred and usual lifestyle of the subject. (Periodic abstinence [eg, calendar, ovulation, symptothermal, postovulation methods] and withdrawal are not acceptable methods of contraception.)

Male patients, even if surgically sterilized (ie, status postvasectomy) must agree to 1 of the following:

- Practice effective barrier contraception during the entire study treatment period and through 90 days after the last dose of study drug, or
- Agree to practice true abstinence, when this is in line with the preferred and usual lifestyle of the subject. (Periodic abstinence [eg, calendar, ovulation, symptothermal, postovulation methods for the female partner] and withdrawal are not acceptable methods of contraception.)

6.6 Management of Clinical Events

Adverse drug reactions such as thrombocytopenia, diarrhea, fatigue, nausea, vomiting, and rash have been associated with ixazomib treatment. Management guidelines regarding these events are outlined below. Further details of management of ixazomib AEs are described in Section 6 of the ixazomib IB.

Prophylaxis Against Risk of Reactivation of Herpes Infection

Patients may be at an increased risk of infection including reactivation of herpes zoster and herpes simplex viruses. Antiviral therapy such as acyclovir, valacyclovir, or other antivirals may be initiated as clinically indicated. Other antivirals are also acceptable.

Nausea and/or Vomiting

Standard anti-emetics including 5-hydroxytryptamine 3 serotonin receptor antagonists are recommended for emesis if it occurs once treatment is initiated; prophylactic anti-emetics may also be considered at the physician's discretion. Fluid deficit should be corrected before initiation of study drug and during treatment.

Diarrhea

Prophylactic antidiarrheals will not be used in this protocol. However, diarrhea should be managed according to clinical practice, including the administration of antidiarrheals once infectious causes are excluded. Fluid intake should be maintained to avoid dehydration. Fluid deficit should be corrected before initiation of treatment and during treatment.

Erythematous Rash With or Without Pruritus

As with bortezomib, rash with or without pruritus has been reported with ixazomib, primarily at the higher doses tested and when given with agents where rash is an overlapping toxicity. The rash may range from limited erythematous areas, macular and/or small papular bumps that may or may not be pruritic over a few areas of the body, to a more generalized eruption that is predominately on the trunk or extremities. Rash has been most commonly characterized as maculopapular or macular. To date, when it does occur, rash is most commonly reported within the first 3 cycles of therapy. The rash is often transient, self-limiting, and is typically Grade 1 to 2 in severity.

Symptomatic measures such as antihistamines or corticosteroids (oral or topical) have been successfully used to manage rash and have been used prophylactically in subsequent cycles. The use of a topical, IV, or oral steroid (eg, prednisone \leq 10 mg per day or equivalent) is permitted. Management of a Grade 3 rash may require intravenous antihistamines or corticosteroids. Administration of ixazomib (and/or other causative agent if given in combination) should be modified per protocol and re-initiated at a reduced level from where rash was noted (also, per protocol).

In line with clinical practice, dermatology consult and biopsy of Grade 3 or higher rash or any SAE involving rash is recommended. Prophylactic measures should also be considered if a patient has previously developed a rash (eg, using a thick, alcohol-free emollient cream on dry

areas of the body or oral or topical antihistamines). A rare risk is Stevens-Johnson Syndrome, a severe and potentially life-threatening rash with skin peeling and mouth sores, which should be managed symptomatically according to standard medical practice. Punch biopsies for histopathological analysis are encouraged at the discretion of the investigator.

Thrombocytopenia

Blood counts should be monitored regularly as outlined in the protocol with additional testing obtained according to standard clinical practice. Thrombocytopenia may be severe but has been manageable with platelet transfusions according to standard clinical practice. A rare risk is thrombotic thrombocytopenic purpura (TTP), a rare blood disorder where blood clots form in small blood vessels throughout the body characterized by thrombocytopenia, petechiae, fever, or possibly more serious signs and symptoms. TTP should be managed symptomatically according to standard medical practice.

Neutropenia

Blood counts should be monitored regularly following administration of ixazomib. Neutropenia may be severe but has been manageable. Growth factor support is not required but may be considered according to standard clinical practice.

Fluid Deficit

Dehydration should be avoided since ixazomib may cause vomiting, diarrhea, and dehydration. Acute renal failure has been reported in patients treated with ixazomib, commonly in the setting of the previously noted gastrointestinal toxicities and dehydration.

Fluid deficit should be corrected before initiation of ixazomib and as needed during treatment to avoid dehydration.

Hypotension

Symptomatic hypotension and orthostatic hypotension with or without syncope have been reported with ixazomib. Blood pressure should be closely monitored while the patient is on study treatment and fluid deficit should be corrected as needed, especially in the setting of concomitant symptoms such as nausea, vomiting, diarrhea, or anorexia. Patients taking medications and/or diuretics to manage their blood pressure (for either hypo- or hypertension) should be managed according to standard clinical practice, including considerations for dose

adjustments of their concomitant medications during the course of the trial. Fluid deficit should be corrected before initiation of ixazomib and as needed during treatment to avoid dehydration.

Posterior Reversible Encephalopathy Syndrome

One case of posterior reversible encephalopathy syndrome, which ultimately resolved, has been reported with ixazomib. This condition is characterized by headache, seizures and visual loss, as well as abrupt increase in blood pressure. Diagnosis may be confirmed by magnetic resonance imaging (MRI). If the syndrome is diagnosed or suspected, symptom-directed treatment should be maintained until the condition is reversed by control of hypertension or other instigating factors.

Transverse Myelitis

Transverse myelitis has also been reported with ixazomib. It is not known if ixazomib causes transverse myelitis; however, because it happened to a patient receiving ixazomib, the possibility that ixazomib may have contributed to transverse myelitis cannot be excluded.

